All participants will complete the website questionnaires in order to standardize collection of our functional outcomes. Practitioners in both arms will not have access to the responses to the patient satisfaction questionnaires (WAI-SR and CSQ-8). The other questionnaire responses of the participants randomized to REVAMP management will be available to the practitioners performing the phone clinic evaluations. Enrolled subjects assigned to the in-person arm will only have access to the website's questionnaires but none of its other features. They will be informed that a research staff member will contact them to schedule their first clinic appointment. None of the questionnaires they complete on the website will be shared with their practitioners. At the time of their in-person clinic visits, these participants will complete the questionnaires that are routinely used as a part of the clinical site's usual care. That information will not be collected for analysis.

**Table 2.** Data collection and action schedule for all participants

Measures & Procedures	Baseline assessment	Initial clinical assessment	AutoCPAP set-up	1-week phone FU	1-month FU assessment	3-month FU assessment
	Week 0	Week 2-4	Week 8	Week 9-12	Week 12	Week 20
Eligibility criteria	In-person					
Informed consent	In-person					
Patient characteristic questionnaire	website					
Functional & QOL questionnaires†	website				website	Website Δ
Therapy process indicators‡		website		website	website	Website Δ
Clinical assessment*		In-person vs phone		Phone	In-person vs phone	In-person vs phone
APAP set-up			DME			
APAP adherence*				Wireless	Wireless	Wireless

DME = home health care company; FU=follow-up; QO =quality of life; Δ=performed every 3 months thereafter to the end of data collection

\* Subjects randomized to in-person management will have in-person clinic evaluations in the sleep center and subjects randomized to REVAMP management will have phone clinic sessions. APAP adherence in both groups will be obtained by wireless modem.

[figure not shown]
† Functional & QOL questionnaires: FOSQ-10, ESS, SF-12, CES-D, and EQ-5D; ‡ Therapy process indicators: WAI, CSQ-8 (performed within 1-week following each encounter)

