**Participant randomization.** Upon completing baseline questionnaires, a computer-generated, blocked randomization scheme in the REVAMP program will automatically allocate eligible participants into one of two groups: *REVAMP management versus in-person management*. Randomization at each site will be programmed by SAS module Proc Plan. Block size at each site will be six subjects so that among each block of six randomized individuals, exactly three will be assigned to each group in a random order. Investigation and management of the two arms of care will be conducted over equal time periods.

**REVAMP pathway.** Following completion of the website questionnaires and the HST, REVAMP participants will be scheduled for an initial phone interview with the *sleep specialist (MD or NP)* (Fig 4). The practitioner will review the results with the subject. *Using the criteria required by the Center of Medicare and Medicaid Services, participants with AHI  $\geq 15$  events/hr and subjects with  $5 \leq AHI < 15$  who have OSA-related symptoms will be diagnosed with OSA.* Those interested in PAP treatment will be prescribed an APAP unit with wireless modem. Subjects with OSA who are found on follow-up to require bilevel PAP and/or supplemental oxygen will continue to participate in Aim 1. Participants testing negative for OSA will be offered usual clinical care to further evaluate their sleep-related symptoms. Participants with a diagnosis of central sleep apnea/Cheyne-Stokes respiration

(CSA/CSR) will be referred to a sleep physician and PSG testing. *Participants without OSA on HST and participants with CSA/ CSR will not be included in the Aim 1 modified intent to treat analysis set but will be included in the primary analysis set of Aim 2 and Aim 3.*

The wireless modem on the home PAP unit sends PAP data daily to the manufacturer's server which in turn exports the data daily to the REVAMP website. The website displays the following information in an easily understandable format: hours of use, amount of air leak, and AHI (Fig. 2). Participants and practitioners can view the data on the REVAMP website. Participants will be instructed to review their results on the website daily. The number of times a subject logs into the website will be tracked.

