The primary analysis will use mixed effects models for longitudinal data which make use of all available scores for each participant at each measurement time and permit adjustment for inter-group differences that are not balanced through randomization. All analyses of mixed models will account for clinical site. For the change in FOSQ score, baseline FOSQ score will also be included as an *a priori* covariate. Factors that are pre-specified as being possible confounders in the association of treatment assignment and outcome are age, sex and race. We anticipate little confounding from these patient-level factors given the blocked randomization scheme to ensure balance between treatment groups. The site by treatment group interaction will not be included and this decision reflects recommendations that differences among treatment group means should be estimated weighting sites according to the amount of information they provide. With this weighted estimate, each within-center estimate is given a weight based upon its precision. A series of mixed models is proposed; each outcome identified in the aims will be rotated individually in the modeling process. We assume that change outcomes will be normally distributed but will check the distribution of each outcome before modeling, and, if necessary, use a generalized linear mixed model to accommodate alternative distributions.

A similar analysis will be conducted to test Hypothesis 1b:  $H_0: \mu_R - \mu_P \leq -0.75$  hr/night vs.  $H_a: \mu_R - \mu_P > -0.75$  hr/night; where  $\mu_R$  and  $\mu_P$  are the mean APAP hr/night of patients receiving REVAMP (R) versus in-person (P) management. If the lower bound of the 95% one-sided confidence interval exceeds the non-inferiority delta of  $-0.75$  hr/night, then the null hypotheses of inferiority can be rejected at  $\alpha=0.05$ .

**Multiple comparisons.** No adjustment for multiple comparisons will be performed to account for testing of two primary hypotheses, since rejection of both non-inferiority hypotheses are necessary to conclude that at-home assessment is not clinically inferior relative to in-lab assessment.

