**Analysis of secondary clinical outcomes in Aim 1.** Secondary outcomes in Aim 1 include changes from baseline to Month 3 in scores of the ESS, SF-12 (physical and mental health components), and CES-D questionnaires. For each secondary outcome, analogous analyses of covariance models will be used to determine least squares adjusted treatment group differences in mean change along with 95% confidence

intervals since non-inferiority deltas are not pre-specified. Baseline values of the outcome measures will be included in their respective ANCOVA models. The above results will be interpreted as hypothesis generating.

**Missing data methods.** The mixed model approach uses information in the covariance matrix of predictors and outcomes over time to implicitly impute missing 3-month FOSQ values. Of note, participants will complete the assessment battery at 1-month following initiation of treatment. Therefore, subjects missing month 3 results will not be excluded. These imputations are valid if the likelihood of missingness is independent of treatment group, conditional on observed data included in the model, i.e., if missing data are missing at random (MAR). For comparison with earlier studies, we will also perform the analyses using the last observation carried forward method. Finally, in sensitivity analyses, we will evaluate the impact of departure from the assumed MAR mechanism by using multiple imputation (MI) to implement a selection model approach. In this way, we will be able to compare estimated effects based on different assumptions about the missingness mechanism, and to assess the sensitivity of our estimates to these assumptions. If data on predictors is incomplete, we will use multiple imputation methods (as implemented in SAS PROC MI and MIANALYZE) to generate multiple imputed complete datasets, perform analyses, and then combine analysis results to produce estimates that are asymptotically unbiased, with standard errors that account for imputation uncertainty.

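### The missing-data section misstates when the mixed model is valid, and the FOSQ-10 analysis leaves out PAP hours, which could bias the non-inferiority estimate in either direction

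*Combined protocol and SAP*

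**What the plan says.** Under STATISTICAL ANALYSIS, the paragraph on missing data methods says that the mixed model implicitly imputes missing 3-month FOSQ values. It gives the condition as "These imputations are valid if the likelihood of missingness is independent of treatment group, conditional on observed data included in the model", and explains this as "i.e., if missing data are missing at random (MAR". Two further analyses are planned: last observation carried forward, and an examination of departures from MAR "by using multiple imputation (MI) to implement a selection model approach". No variables, parameters or range are given for the latter. PROC MI is reserved for incomplete predictors.

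The paragraphs on the non-inferiority hypotheses set out the model. "All analyses of mixed models will account for clinical site", and "baseline FOSQ score will also be included as an" a priori covariate. The possible confounders named in advance for the "association of treatment assignment and outcome are age, sex and race". The search for further covariates, described under the baseline comparisons, covers baseline factors only. Each outcome is modelled separately.

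PAP hours are collected without any questionnaire. The REVAMP pathway text says "The wireless modem on the home PAP unit sends PAP data daily", and the footnote to Table 2 says "APAP adherence in both groups will be obtained by wireless modem". They are the outcome for Hypothesis 1b. No FOSQ-10 model or imputation step names them.

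**The concern.** Treatment group is a term in the model, so missingness may depend on it without harm. What matters is whether, within an arm and given the data the model uses, people who miss month 3 would have scored differently from those who respond. The stated condition does not address this.

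The second half follows from the first. MAR is only as credible as the list of observed data in the model. How much a participant uses PAP is an obvious candidate for driving both FOSQ-10 change and willingness to fill in a questionnaire, and the trial holds that variable in both arms. Without it, the model has only the 1-month score, baseline FOSQ-10, site and perhaps demographics to explain non-response.

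The link could differ by arm. REVAMP participants are told to review their PAP data on the website that carries the questionnaires, and they receive its reminders. In-person participants can open only the questionnaires. Someone in REVAMP who abandons PAP might therefore abandon the questionnaires too. That is an inference from the design; the documents offer no evidence for it. At stake is the error rate of the primary non-inferiority test.

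**Working it through.** **The plan's own figures.** Margin 1, SD 2.80, one-sided alpha 0.05, power 85%: n = 2 × (1.645 + 1.036)² × 2.80² / 1² = 112.7, so 113 per group. The exact t calculation first reaches 85% at 114 (85.2%), as stated. Enrolment is 228 / 0.8 / 0.8 = 356.25, against 356 stated. These figures reproduce and are not in dispute. APAP starters per arm are 114 / 0.8 = 142.5; 142 is used below.

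**Is the stated condition necessary?** No. With drop-out of 10% in one arm and 30% in the other, depending on arm alone or on arm and the observed 1-month score, the condition fails. Simulated bias was nevertheless +0.006 to +0.015 points, and the probability of declaring non-inferiority at a true difference of -1 was 0.050 to 0.053.

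**Is it sufficient as a guard?** Equal drop-out by arm is not. A hand calculation shows why. Inputs from the plan: SD 2.8 for FOSQ-10 change, SD 2.2 for hours, 20% drop-out. Assumptions not in the documents:
- correlation of 1-month with 3-month change: 0.6
- correlation r of hours with 3-month change: 0.2 to 0.5
- correlation of hours with 1-month change: 0.7r
- drop-out in one arm follows a logistic model with slope 1.5 per SD of hours
- drop-out in the other arm is random
- hours do not differ by arm

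Solving the logistic intercept for 20% drop-out puts non-responders 0.906 SD below their arm's mean hours (0.906 × 2.2 = 2.0 hr/day). Responders are then 0.2 × 0.906 / 0.8 = 0.227 SD above it. With the 1-month score in the model but not hours:

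bias ≈ 2.8 × (r − 0.6 × 0.7r) × 0.227

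- r = 0.2: 2.8 × 0.116 × 0.227 = 0.07
- r = 0.3: 2.8 × 0.174 × 0.227 = 0.11
- r = 0.5: 2.8 × 0.290 × 0.227 = 0.18

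If all drop-out comes before any follow-up FOSQ-10, the 1-month score cannot help. The bias is then 2.8 × r × 0.227 = 0.13, 0.19 and 0.32. Participants with no follow-up score are excluded from the primary analysis set.

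**Simulation.** 142 per arm, true difference -1, 20% drop-out in each arm, nominal error 0.05. Ranges run over r = 0.2, 0.3, 0.5 and, in the first three rows where varied, over how much drop-out precedes the 1-month score. NI means non-inferiority declared on Hypothesis 1a. The row on the unseen FOSQ-10 uses r = 0.3.

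| What drives drop-out | Bias, hours omitted | P(NI) | Bias, hours auxiliary | P(NI) |
|---|---|---|---|---|
| Low hours, same in both arms | -0.012 to +0.007 | 0.041–0.065 | -0.013 to +0.007 | 0.043–0.065 |
| Low hours in REVAMP only | +0.067 to +0.299 | 0.066–0.220 | -0.013 to +0.007 | 0.038–0.070 |
| Low hours in-person only | -0.089 to -0.262 | 0.008–0.036 | -0.014 to +0.010 | 0.052–0.057 |
| Unseen 3-month FOSQ-10, REVAMP only / in-person only | +0.406 / -0.411 | 0.346 / 0.003 | +0.385 / -0.389 | 0.337 / 0.003 |

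Bias values within about 0.02 of zero are simulation noise. The error of P(NI) is about 0.007 near 0.05 and 0.015 near 0.35.

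**Sensitivity.** A repeat under other assumed inputs gave +0.06 to +0.27 for REVAMP only and -0.05 to -0.18 for the mirror case. It gave +0.03 to +0.08 when the in-person slope was half as strong. At the other extreme, if low hours drove drop-out in REVAMP and high hours drove it in-person, the bias was +0.192 to +0.492; nothing in the documents suggests that pattern.

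**The case against.** The strongest reply has five parts.

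- **The sentence is a wording error.** It names MAR, it conditions on observed data, and correcting it changes no estimate. This stands.
- **The plan already has a safeguard.** The selection-model analysis targets departures from MAR, including missingness driven by the unseen FOSQ-10, where PAP hours barely help (+0.406 becomes +0.385). This stands, and that analysis deserves credit. It is unspecified, though, and plays no part in the decision rule.
- **The sizes depend on the scenario.** With a slope of 1 per SD, and hours correlated with 1-month change as strongly as with 3-month change, the one-arm bias falls to 0.06 to 0.13 points. This stands, which is why a range is given.
- **Hypothesis 1b must also pass, and it tests PAP use directly.** This protects in part. If mean hours are equal, 1b passes about 82% of the time at 114 per group, so it would seldom block a biased result on 1a.
- **The documents do not say that modem data are kept after a participant stops answering questionnaires.** This stands as an assumption of the fix.

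A reader might infer that equal drop-out would hide a bias toward non-inferiority, or that the plan would accept equal drop-out as proof of validity. The documents support neither. No comparison of drop-out rates is planned to justify MAR; attrition is compared only as an acceptability outcome in Aim 3. Equal overall rates would not meet even the stated condition, which is conditional on observed data. The bias also needs a mechanism that differs by arm, and it can run against REVAMP as easily as for it.

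**Conclusion.** The concern holds in a conditional form. The validity condition is wrongly stated, and PAP hours are absent from the FOSQ-10 missing-data model although they are collected in both arms. If low hours drive non-response in one arm only, the estimate could be biased by about 0.05 to 0.3 points, or 5% to 30% of the margin, in either direction and with equal drop-out. That range assumes correlations of 0.2 to 0.5 between hours and 3-month change, and of 0.5 to 0.6 between 1-month and 3-month change. A weaker contrast between arms gives less, and the same mechanism in both arms gives about zero. The error rates above are for Hypothesis 1a alone, not for the joint conclusion. The plan should be amended on this point, but nothing here shows that the trial's result will be biased.

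**What to change.** 1. Restate the condition: the mixed model is valid if missingness does not depend on the unobserved 3-month FOSQ-10, given treatment group and the observed data in the model.
2. Pre-specify multiple imputation of month-3 FOSQ-10, run separately by arm. Use PAP hours per day (month 1, and months 2–3), 1-month FOSQ-10 and 1-month ESS as auxiliary variables. Keep PAP hours out of the outcome model: they arise after randomization, and adjusting for them would change the treatment effect being estimated.
3. State whether modem data are retained after questionnaires stop. State also whether the imputation covers APAP starters with no follow-up FOSQ-10; if it does not, PAP hours cannot help with those participants.
4. Keep the selection-model analysis for missingness that depends on the unseen FOSQ-10, and name its variables and range of parameters, by arm.

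The cost is a corrected sentence, a few lines of specification and one additional imputation model. It needs no new data collection, and PROC MI is already in the plan.

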Following the first week of PAP treatment, a therapist with at least one year of experience managing patients with OSA will phone the participant. Using a standardized protocol, the therapist will evaluate the participant's response to treatment, inquire if any barriers are limiting PAP use, and provide advice on how to overcome those problems (see *Appendix 4*). The therapist will encourage the participant to review his/her PAP data on the website. The participant will be scheduled for 1- and 3-month follow-up phone calls with the therapist. Additional phone calls are allowed as clinically indicated and will be tracked. The therapist will have the option of consulting with the sleep specialist (MD or NP). Upon consultation, if it is felt that the problem cannot be addressed by phone, the participant will be scheduled for an in-person clinic appointment with the physician. The type, number

and duration of all encounters will be recorded in case report forms. All phone clinic sessions and other patient encounters will be documented in the participant's electronic medical record.

REVAMP has a secure message system that sends e-mail and text messages to the participant alerting him/her to login to the website to view a message. The REVAMP website will use this feature to remind the participant to complete questionnaires, view their PAP data, and keep scheduled phone clinic appointments.

*In-person management.* Participants in the in-person arm will be scheduled to meet with the sleep therapist for in-person set-up instructions for HST. Following HST, a sleep specialist (MD or NP) will conduct the initial in-person clinic evaluation. Participants diagnosed with OSA (using the same criteria detailed above for the REVAMP pathway) who are willing to start PAP treatment will be prescribed APAP. Sleep therapists with at least one year of experience managing patients with OSA will perform the follow-up clinic evaluations. Participants will receive a 1-week phone call and be scheduled for 1- and 3-month in-person follow-up clinic visits. Additional phone calls and clinic visits will be allowed as clinically indicated. The type, number and duration of all encounters will be monitored and documented in the participant's electronic medical record.

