All practitioners will have access to the participant's daily APAP data at the manufacturer's HIPAA compliant, password protected web-site (EncoreAnywhere, Philips-Respiration, Inc or AirView, ResMed, Inc). Participants in the REVAMP arm and their practitioners will also be able to view the PAP data on the REVAMP website. When clinically indicated, adjustments to the APAP pressure range will be made either at the time of the in-person clinic visit or by entering this modification on the manufacturer's website that will reset the participant's APAP device by transmitting the information to the home unit via the wireless connection. Participants will be informed if the pressure range is adjusted. Subjects who unable to tolerate APAP or refuse treatment will be seen by a sleep physician for further evaluation and management.

Blinding of research personnel. Given the differences in management of the two groups, the research personnel cannot be blinded to a participant's group assignment. The practitioners delivering care will not be involved with scoring the HSTs and all of the participant questionnaires are self-administered. The practitioners will not have access to the patient satisfaction questionnaire results or to the data collected for Aims 2 and 3.

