## OUTCOME MEASURES

### Aim 1 – Outcome Measures (see Appendix 3 for validated questionnaires)

Subject Characteristics Questionnaire is a 15-min self-administered and provides the following information: sleep-related complaints, history of risk factors for sleepiness, past medical history, education level, employment status, current medication use, and an assessment of health literacy.

Functional Outcomes of Sleep Questionnaire (FOSQ-10). The FOSQ-10, a disease-specific questionnaire and our primary outcome measure, will be used to compare functional benefit from APAP treatment. The 10-question instrument has been used in research and clinical practice to measure the impact of daytime sleepiness on activities of daily living. FOSQ-10 has an internal consistency of  $\alpha = 0.87$  and a pre-treatment correlation with the total FOSQ (36 questions) of  $r = 0.96$ . After 3 months of CPAP treatment the correlation was  $r = 0.97$ . Effect sizes with treatment for both instruments were highly correlated and indicate ability to measure meaningful change. Differences were observed between FOSQ-10 scores for normal controls and OSA patients. The measure is at a 5th grade reading level and takes less than 5 min to complete.

APAP adherence will be objectively monitored by exporting the data from the REVAMP website. Average hours per day of APAP use over the initial 3 months of treatment will be used to test our hypothesis that participants who receive telemedicine-based versus in-person care have similar APAP adherence. In addition to adherence data, the APAP units provide information on treatment efficacy.

Epworth Sleepiness Scale Questionnaire (ESS) assesses perceived daytime sleepiness and will be used to test our hypothesis that participants in the two arms have similar improvements in subjective daytime sleepiness (change in person level disability) on PAP therapy. The respondent rates the likelihood of falling asleep in eight soporific situations using a 4-point Likert scale ranging from “never dozing” to “high chance of dozing”. Multiple RCTs report a reduction in ESS with PAP therapy in OSA patients.

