**Statistical methods for non-inferiority hypotheses.** Aim 1 will determine if REVAMP management is not clinically inferior to in-person treatment, in terms of the difference between baseline and post-treatment FOSQ score (Hypothesis 1A), and mean APAP use (Hypothesis 1B). To test the Aim 1 hypotheses, we will use a modified intent to treat analysis set, i.e., participants with a diagnosis of OSA who were treated with PAP with or without supplemental oxygen. This strategy will avoid potential bias in the non-inferiority analysis of treatment effect. To demonstrate non-inferiority for Hypothesis 1a we will test the primary non-inferiority hypothesis:  $H_0: \Delta_{R-P} \leq -1$  vs.  $H_a: \Delta_{R-P} > -1$ ; where  $\Delta_R$  and  $\Delta_P$  are the mean FOSQ-10 change scores from baseline to 3 months in the REVAMP (R) and in-person (P) groups, respectively, and where a positive change score indicates improvement. In these equations we have explicitly included the value of the pre-specified non-inferiority margin,  $\delta=1$ , for change in FOSQ score. The hypothesis will be tested by using analyses of covariance to construct least squares estimates of the (adjusted) group differences in mean values along with their 90% confidence intervals (CI). The lower bound of the 90% CI is equivalent to the lower bound of a 95% one-sided non-inferiority CI. If the lower bound exceeds the *a priori* non-inferiority delta, then the null hypotheses of inferiority can be rejected at  $\alpha=0.05$ .

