**Modified intent-to-treat and per-protocol populations.** Primary analysis for non-inferiority will be based on all randomized participants initiated on APAP with at least one FOSQ follow-up score. In a secondary analysis, the non-inferiority test will be repeated using a per protocol cohort (patients who have been initiated on APAP and have non-missing endpoints at month 3), since protocol violations can add noise making it more difficult to distinguish between the two active treatment groups.

**Statistical methods for Aim 2.** Aim 2 will determine if REVAMP management of patients with OSA is cost-effective compared with in-person care. The perspective of the analysis will be that of the VA. While the VA has the general well-being of veterans as its goal, we will focus our attention on health care costs, in part because VHA patients with OSA are older and less likely to work. The analyses for Aim 2 will be based on all randomized participants, as this is the target population for the evaluation of Aim 2 and Aim 3 outcomes related to management of this patient population. We will perform a secondary analysis using the modified intention to treat sample (Aim 1 analysis set). The primary outcome measure in Aim 2 will be the difference in sleep-related cost between the two delivery modalities. Our hypothesis is 2a)  $H_0: \Delta C = 0$  vs  $H_A: \Delta C < 0$ . Based on data from our prior study of home vs in-lab diagnosis, we assume average 3-month sleep-related costs of \$1755 (SD, 745) for the home group and of \$2538 (SD, 1065) for the in-lab group. Resulting power is 1.0 for sample size of 114 per group and remains greater than 0.9 if, when including participants without OSA on HST and participants with CSA/CSR, the means are reduced by 25% and the SDs are increased by 25%.

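### Aim 1 non-inferiority is tested only in participants who started PAP, so a difference in PAP uptake cannot show in Hypothesis 1b; the two definitions of the analysis set also disagree on a FOSQ-response condition

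*Combined protocol and SAP*

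**What the plan says.** **Timing.** Randomization comes first (Participant randomization): "Upon completing baseline questionnaires, a computer-generated, blocked randomization scheme in the REVAMP program will automatically allocate eligible participants". Home sleep testing, diagnosis and the PAP decision follow. The consultation at which PAP is offered is by phone under REVAMP and in clinic in the other arm.

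**Who starts.** Under REVAMP, "Those interested in PAP treatment will be prescribed an APAP unit with wireless modem". In the in-person arm, PAP goes to diagnosed participants "who are willing to start PAP treatment will be prescribed APAP". The section on PAP treatment adds: "Subjects who unable to tolerate APAP or refuse treatment will be seen by a sleep physician".

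**Analysis set.** Two sections define it.
- Statistical methods for non-inferiority hypotheses applies one set to the Aim 1 hypotheses together: "participants with a diagnosis of OSA who were treated with PAP with or without supplemental oxygen". It gives the reason: "This strategy will avoid potential bias in the non-inferiority analysis of treatment effect".
- Modified intent-to-treat and per-protocol populations says: "Primary analysis for non-inferiority will be based on all randomized participants initiated on APAP with at least one FOSQ follow-up score". The per-protocol repeat keeps APAP starters with month-3 endpoints, which is narrower.

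**Endpoint.** Adherence for 1b is "Average hours per day of APAP use over the initial 3 months of treatment", taken from the wireless modem. Both 1a and 1b must be met to conclude non-inferiority (Multiple comparisons).

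**The concern.** Whether a diagnosed patient starts PAP can depend on how the consultation was delivered, and that is what the trial compares. Neither stated set for the non-inferiority tests includes a diagnosed participant who never starts. Hypothesis 1b is worded for patients receiving one form of management or the other, but hours during treatment have no value for a non-starter. An arm could therefore lose patients at the uptake step and show no deficit in 1b.

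The plan's bias argument is sound for dilution: untreated participants pull FOSQ-10 changes together and favour a non-inferiority finding. It does not cover selection through uptake that differs by arm.

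Separately, two analysts following the two sections would build different primary sets. Only one section requires a follow-up FOSQ-10 score, and it does not limit that condition to 1a. Only the other names an OSA diagnosis, and it says PAP where the first says APAP.

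**Working it through.** **Inputs.** From Sample size, and power: 1a margin 1.0, SD 2.80; 1b margin 0.75 h/day, SD 2.2, pilot mean 5.3 h/day; 114 per group; 20% without OSA; 20% drop-out among APAP starters; 356 enrolled. From Statistical methods for non-inferiority hypotheses: one-sided 0.05. Uptake by arm is not given and is assumed below. It is also assumed that 5.3 h applies to starters, since the plan attributes it to participants enrolled in the pilot.

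**1. The plan's own figures.** Power by non-central t at 114 per group is 85.2% for 1a (stated: at least 85%) and 82.2% for 1b (stated: 80%). Enrollment is 228/(0.80 × 0.80) = 356.25. These reproduce. The calculation has no factor for diagnosed participants who never start.

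**2. Uptake gap equal to the margin.** If starters average m hours in both arms and non-starters count 0 h, the difference over all diagnosed is m × (uptake REVAMP − uptake in-person). Setting it to −0.75 gives a gap of 0.75/m:
- m = 5.3: 14.2 points
- m = 4: 18.8 points
- m = 6: 12.5 points

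For FOSQ-10, with a mean gain of about 1.8 (the prior study's 1.74 and 1.85) and non-starters unchanged, the gap would be 1/1.8 = 56 points. The issue is therefore mainly with 1b.

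**3. What each analysis would conclude.** Diagnosed per arm: 356 × 0.8/2 = 142. Per-arm variance with zeros: V(u) = u × 2.2² + u(1 − u) × 5.3². Simulation used 40,000 trials, starters alike in both arms, pooled t, and no loss among starters.

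| Uptake, REVAMP vs in-person (assumed) | True difference, all diagnosed | Passes, starters only | Passes, all diagnosed |
|---|---|---|---|
| 90% vs 90% | 0 | 85.7% | 77.6% |
| 80% vs 80% | 0 | 82.3% | 70.5% |
| 85% vs 90% | −0.27 h | 85.1% | 44.9% |
| 80% vs 90% | −0.53 h | 84.1% | 16.1% |
| 75.8% vs 90% | −0.75 h | 83.0% | 5.0% |

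If 20% of starters are lost from 1b, the starters-only figure is 78.0% at 90% in both arms, 74.1% at 80% in both, and 75.2% at 75.8% vs 90%. The contrast remains.

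**4. Limits of the all-diagnosed estimate.** The SD is √V = 2.62 at 90% uptake and 2.89 at 80%, so the 90% CI half-width is 0.51 h or 0.57 h. With equal uptake u, a true −0.75 h among starters shrinks to −0.75u. The estimate would then clear the margin in 8.0%, 11.5% or 15.7% of trials at 90%, 80% or 70% uptake, against 5% for starters only.

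**5. Planned size.** Applying the plan's 20% drop-out to starters leaves 142 × 0.9 × 0.8 = 102 per arm, or 142 × 0.8 × 0.8 = 91. If drop-out removes the data, 1a/1b power is about 82%/78% or 77%/74%.

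**6. FOSQ condition.** Shift in 1b = (difference between arms in non-response) × (responder minus non-responder hours). With an assumed 10 points and 2 h, that is 0.10 × 2 = 0.2 h, and 0.2/0.75 = 27% of the margin. Both inputs are assumptions.

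**The case against.** The strongest reply is that this is a choice of estimand. The plan defines adherence during treatment, treated-only sets are common in non-inferiority work, and no document shows an uptake gap. Diagnostic criteria, test interpretation blinded to arm, and home delivery of the unit are common to both arms. This stands: the treated-only test should remain primary, and the gaps above are illustrations.

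The plan also has partial safeguards. It tracks why participants could not complete the protocol, uses all randomized participants for Aim 2 costs and QALYs, and makes drop-out an Aim 3 outcome. None enters the 1b decision, and the drop-out outcome does not say whether never starting counts.

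Applying the FOSQ condition to 1b is the harshest reading, since FOSQ-10 is the primary outcome and one month-1 score keeps a participant in the set. That makes it a wording fix, but the text does not limit the condition to 1a. The sentence on intolerance or refusal may also concern people already on a device; the interest and willingness wording is firmer evidence that non-starters are expected.

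Three stronger readings are tempting but unsupported:
- *The planned 1b test has an inflated type I error, or favours REVAMP.* It does not follow. The all-diagnosed mean is a different estimand, and the direction of any gap is unknown.
- *Planned size absorbs non-uptake.* That holds only if no starter's data are lost. The plan itself allows 20% drop-out among starters, and power then falls below the stated 85%/80%.
- *The FOSQ condition has a calculable power cost.* Comparing 20% loss with zero loss overstates it, because the plan already allows 20%.

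**Conclusion.** The point holds on the text. The primary and per-protocol non-inferiority sets both depend on a step after randomization that follows arm-specific care, so a difference in PAP uptake cannot appear in 1b. The plan's claim to avoid bias covers dilution only. The two definitions of the set conflict on the FOSQ condition, and that part needs no assumption.

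The size is conditional. A 14-point uptake gap would equal the 0.75 h margin if starters use 5.3 h and non-starters count as 0 h (12.5 to 19 points for 6 to 4 h). The effect on 1a is modest. The documents do not show that such a gap exists or which arm it would favour. A 1b result from the planned test supports a conclusion about participants who started PAP, not about everyone diagnosed under each form of management.

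**What to change.** 1. State one definition of the Aim 1 set in both sections, and say that the FOSQ condition does not apply to 1b.
2. Keep the treated-only 1b test as primary. State, without conditions, that its conclusion applies to participants who started PAP.
3. Add a supportive, descriptive 1b estimate with 90% CI in all randomized participants diagnosed with OSA, as assigned, with non-starters at 0 h. Show it next to −0.75 h with no pass/fail rule.
4. Tabulate OSA diagnosis, PAP start and FOSQ response by arm, with a CI for the uptake difference, adding to the planned tracking and the Aim 3 drop-out outcome. With 142 per arm the 95% half-width is 1.96 × √(2 × 0.9 × 0.1/142) = 7.0 points at 90% uptake, and 9.3 at 80%. The table is needed because the all-diagnosed set still conditions on diagnosis, which follows arm-specific set-up of the home test.
5. Limit the bias statement to dilution.

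**Cost.** Wording, one added model and one table, with no change to sample size, conduct or the primary test. The supportive estimate is less precise (about 78% or 70% power at equal uptake of 90% or 80%) and dilutes a true deficit among starters, so it cannot replace the primary.
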